6.4.1 Medical History

Medical history will be coded according to Medical Dictionary for Regulatory Activities (MedDRA) version 22.1 or higher and will be displayed by system organ class and preferred term, using the MedDRA internationally agreed order.

The numbers and percentages of subjects with medical history will be presented by MedDRA system organ class (SOC) and preferred term (PT) by vaccine group and overall. Medical history data will be tabulated for Enrolled Set.

For prior vaccination history, the number and percentage of subjects who have ever been vaccinated, who have received at least 2 Seasonal Influenza Vaccinations prior to current influenza season and who have been assigned to receive 1 or 2 vaccinations during the study, based on the previous vaccination history, will be summarized.

Adverse events that occur between the time the ICF was signed and administration of first vaccination are recorded on the AE form. These events will be reported as an output in the Medical History.

6.4.2 Prior and Concomitant Medications

Medications will be coded using the WHO Drug dictionary version B3 MARCH 2019 or higher.

A prior medication is a medication used only before the first study vaccination (i.e. medication end date < first study vaccination date). Concomitant medications are all medications taken during the study period, including those started before but ongoing at vaccination.

When start and/or end dates of a medication intake are missing, the medication is considered as concomitant with the study vaccination schedule.

If the study vaccination date is missing, then the medication is considered as concomitant with the study vaccination schedule, provided that the study vaccine was administered to the subject.

Use of concomitant medication will be tabulated by treatment, age cohort, therapeutic area, and preferred drug name on the Enrolled Set.

Prior medications will only be listed.

6.5 Efficacy

6.5.1 Primary Efficacy Endpoints Analysis

The primary efficacy analysis will be based on the FAS Efficacy. Eligible subjects for FAS analysis are subjects who are randomized and received at least one study vaccine and will be analyzed according to their randomized study vaccine (intent-to-treat analysis). Absolute vaccine efficacy will only be assessed for RT-PCR confirmed influenza episodes (primary efficacy endpoint 1a) and culture confirmed antigenically matched influenza episodes (primary efficacy endpoint 1b) with first onset of illness occurring at > 14 days after the last vaccination was administered in the treatment period until the end of the influenza season. Additionally, the primary objective will be evaluated in PPS Efficacy.

Time-to-event methodology based on a proportional hazard model will be used for all efficacy analyses to estimate the hazard ratio (HR). Absolute vaccine efficacy (aVE) against first occurrence RT-PCR confirmed influenza cases will be determined using a standard formula: $aVE = 1 - HR$ where HR is the hazard ratio for RT-PCR influenza confirmed cases in the QIVc group versus the comparator group. The HR will be estimated by a proportional hazards regression model, described below. For which the following null (H0) and alternative (H1) hypotheses will be tested:

$$H_0: 1 - HR \leq 0 \text{ versus } H_1: 1 - HR > 0$$

where HR is a hazard ratio of QIVc versus comparator and VE is vaccine efficacy. For both primary efficacy objectives, the HR and the related 97.5% CI of HR, for onset of first RT-PCR confirmed influenza will be estimated by a proportional hazards regression model with treatment effect as a fixed effect and stratifying covariates as random effect:

$$h_i(t|X) = h_0(t) \exp(\beta^T X + b^T Z),$$

with t denoting time to the influenza, β is the effect of treatment group indicated by X , b is random effect (assumed as a multivariable random gaussian variable with zero mean and diagonal covariance matrix), Z is random effect covariate (reflecting randomization strata).

Subjects that did not experience an event during observation period (be > 14 days after last vaccination up to end of influenza season) and subjects that dropped out from the study during observational period will be censored (right censoring) at the last available date in the eCRF prior to the end of influenza season.

The estimate of the hazard ratio, the respective estimate for absolute VE and the pertaining two-sided CIs will be calculated based on this model, including treatment group (2 treatments), age strata (2 categories, 6 through 23 months or 24 through 47 months), gender (male or female), vaccination history (yes or no) and country. If

Statistical Analysis Plan – Final v2.0

Sponsor Name: Seqirus UK Limited
Sponsor Protocol ID: V130_14

the study continues over several seasons, estimates will be also adjusted for the factor season(s).

In case of one or two (interim) analyses, confidence levels at each stage will be adjusted to provide 97.5% overall coverage.

For each of the multiple primary objectives, estimates for hazard ratio in Cox Proportional Hazard (PH) model will be calculated using Maximum Likelihood (ML) method. In case of problems with convergence (algorithm does not converge or converges to infinite estimates) penalized ML approach will be used (Heinze and Schemper).

Vaccine efficacy $VE = 1 - HR$, that is, $1 - \exp(\hat{\beta})$ with $\hat{\beta}$ with $100(1 - \alpha)$ percent confidence interval as: $[1 - \exp(\hat{\beta}) + Z(\text{s.e.}(\hat{\beta}))]; [1 - \exp(\hat{\beta}) - Z(\text{s.e.}(\hat{\beta}))]$. Z is the $100(1 - \alpha)$ percent point of the standard normal distribution, and s.e. denotes the standard error of β .

The hazard ratio is the predicted ratio of cases of Influenza A and/or B disease in subjects receiving QIVc and comparator within each of the strata of interest. The term β_g is the estimate of treatment effect (or regression coefficient) between QIVc and comparator within each of the stratum.

The estimate of the hazard ratio, the respective estimate for absolute VE and pertaining two-sided 97.5% CIs will be calculated based on this model. If the study continues over several seasons, estimates will be also adjusted for the factor season(s). Factor country might be added to the model if appropriate. In case of more than one interim analysis confidence level for the estimates at the final stage will be adjusted. In case interim analyses will be performed a k-stages group - sequential test procedure for time-to-event data will be implemented. As the K-stage interim analysis for absolute VE introduces a multiple test problem, alpha will be adjusted as described in Section 6.8 Interim Analysis via an error-spending function. For this group sequential test procedure parameters like information level and/or standard error at each stage will be calculated by the above described model and then used to calculate the actual group sequential test that compared the test statistic at each stage with the respective boundaries. Repeated CIs for each stage and also the final estimator and the respective CI can be retrieved by the group sequential test method to maintain simultaneous coverage probability.

Success Criteria for the Multiple Primary Efficacy Objectives:

The primary objective of efficacy is considered demonstrated if efficacy is demonstrated for at least one of the two primary efficacy endpoints, if the lower limit of the two-sided 97.5% CI of VE is greater than 0% in subjects 6 months through 47 months of age.

Statistical Analysis Plan – Final v2.0

Sponsor Name: Seqirus UK Limited
Sponsor Protocol ID: V130_14

In case an interim analysis will be performed the 97.5% CI will be adjusted accordingly. If an interim analysis is performed and the trial continues, then all the subsequent analysis will be tested at a reduced alpha level, i.e. what's left from the interim analysis.

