#### **8.4.2.2.3 Statistical Methods**

For both primary efficacy objectives, the HR and the related 97.5% CI of HR, for onset of first RT-PCR confirmed influenza will be estimated by a proportional hazards regression model with treatment effect as a fixed effect and stratifying covariates as random effect:

$h_i(t|X) = h_0(t) \exp(\beta^T X + b^T Z)$ , with  $t$  denoting time to the influenza,  $\beta$  is the effect of treatment group indicated by  $X$ ,  $b$  is random effect (assumed as a multivariable random gaussian variable with zero mean and diagonal covariance matrix),  $Z$  is random effect covariate (reflecting randomization strata, see SAP for further discussion of the covariates utilized).

Subjects that did not experience an event during observation period and subjects that dropped out from the study during observational period will be censored (right-censoring).

The estimate of the hazard ratio, the respective estimate for absolute VE and the pertaining two-sided CIs will be calculated based on this model.

If the study continues over several seasons, estimates will be also adjusted for the factor season ( $s$ ). In case of one or two (interim) analyses, confidence levels at each stage will be adjusted to provide 97.5% overall coverage.

For each of the multiple primary objectives, estimates for hazard ratio in Cox Proportional hazard (PH) model will be calculated using Maximum Likelihood (ML) method. In case of problems with convergence (algorithm does not converge or converges to infinite estimates) penalized ML approach will be used (Heinze and Schemper).

Vaccine efficacy  $VE = 1 - HR$ , that is,  $1 - \exp(\hat{\beta})$  with  $\hat{\beta}$  with  $100(1 - \alpha)$  percent confidence interval as:  $[1 - \exp(\hat{\beta} + Z(s.e.(\hat{\beta}))); 1 - \exp(\hat{\beta} - Z(s.e.(\hat{\beta})))]$ .

$Z$  is the  $100(1 - \alpha)$  percent point of the standard normal distribution, and s.e. denotes the standard error of  $\hat{\beta}$ .

The hazard ratio is the predicted ratio of cases of Influenza A and or B disease in subjects receiving QIVc and comparator within each of the strata of interest. The term  $\beta_g$  is the estimate of treatment effect (or regression coefficient) between QIVc and comparator within each of the stratum.

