All subjects, irrespective of previous influenza vaccination history, will receive 1 safety follow-up call 90 days after last vaccination during the follow up period and the follow-up period will conclude with a study completion visit (clinic visit or call). All subjects aged 6 through 11 months at enrollment, irrespective of randomization to investigational or comparator group, will receive a dose of the MenC vaccine at the end of the study.

The timing and frequency of the study visits are described in Schedule of Assessments ([Appendix A](#)).

The treatment arms of Study Vaccine comprise:

Study treatment:

Subjects who meet the entry criteria will be stratified by age and vaccination history and then randomized to one of the two treatment groups using a 1:1 allocation ratio to receive either Seqirus QIVc or the MenC-vaccine.

Investigational treatment

A cell-derived quadrivalent inactivated subunit influenza vaccine (QIVc) will be used as investigational vaccine.

Vaccination schedule:

- Subjects ≥ 12 months with a previous influenza vaccination history: One dose of QIVc at Visit 1.
- Subjects ≥ 12 months without a previous influenza vaccination history and subjects 6 through 11 months: One dose of QIVc at Visit 1 followed by one dose of QIVc at Visit 2.

Comparator treatment:

Meningococcal Group C Polysaccharide Conjugate Vaccine (MenC vaccine, Neisvac-C, Pfizer) will be used as a comparator.

Vaccination schedule:

- Subjects ≥ 12 months with a previous influenza vaccination history: One dose of MenC vaccine at Visit 1.
- Subjects ≥ 12 months without a previous influenza vaccination history and subjects 6 through 11 months: One dose of MenC vaccine at Visit 1 followed by one dose of placebo (saline for injection) at Visit 2.
- All subjects aged 6 through 11 months at enrollment, regardless of treatment assignment, will receive a dose of the MenC vaccine at Visit 5.

Statistical Analysis Plan – Final v2.0

Sponsor Name: Seqirus UK Limited
Sponsor Protocol ID: V130_14

Withdrawn Subjects

Subjects may withdraw from the study at any time at their own request or request of the parent or legally appropriate representative, or they may be withdrawn at any time at the discretion of the investigator should any untoward effects occur and/or for safety reasons.

The reasons for premature withdrawal from the study include the following:

- Adverse event (AE)
- Death
- Withdrawal of consent
- Lost to follow-up
- Other
- Protocol deviation

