Appendix B: Example SAS® code for analyses

- **Tables that need descriptive statistics – continuous variables:**

```
PROC UNIVARIATE DATA=dset NOPRINT;  
  VAR var1 var2 var3 ...varn;  
  BY byvar; (optional)  
  OUTPUT OUT=outname  
  N=n MEAN=mean MIN=min MAX=max MEDIAN=median STD=std;  
RUN;
```

- **Tables that need frequency counts:**

```
PROC FREQ DATA=dset NOPRINT;  
  BY byvar; (optional)  
  TABLES var1*var2;  
  OUTPUT OUT=outname;  
RUN;
```

- **Tables that need exact 95%CIs between groups for proportions:**

```
PROC FREQ DATA=dset;  
  BY byvar; (optional)  
  TABLES var1 * var2 / binomial(exact) MEASURES ALPHA=0.05;  
RUN;
```

Notes: 1 Estimates are computed for 2x2 tables only

2 This code also gives exact 95% CIs within group for binomial proportions

- **Tables that need 95% CIs within group for binomial proportions:**

```
PROC FREQ DATA=dset;  
  BY byvar; (optional)  
  TABLES var1;  
  EXACT BINOMIAL;  
RUN;
```

- **Code to create 97.5% CIs within group for continuous variables:**

```
DATA outdata;  
  SET outname;  
  LCL=mean-(TINV(0.975,n-1)*(std/SQRT(n)));  
  UCL=mean+(TINV(0.975,n-1)*(std/SQRT(n)));  
RUN;
```

- **Table to estimate the Hazard Ratio (HR) for all Efficacy Analysis:**

```
PROC PHREG DATA=data;  
  MODEL (T1) *CENSOR(0)= trt agegrp vachis /rl alpha=0.025;  
  RANDOM agegrp vachis; STRATA trt;  
RUN;
```

- **General linear model (adjusted analysis):**

Statistical Analysis Plan – Final v2.0

Sponsor Name: Seqirus UK Limited
Sponsor Protocol ID: V130_14

```
PROC GLM DATA= dset OUTSTAT=outset;  
  CLASS classification variables;  
  MODEL <log transformed response> = <treatment group> <Age group>  
  <Sex><vaccination history> <log transformed base> <siteid>  
  <agegroup*treatmentgroup> / SOLUTION;  
  LSMEANS treatmentgroup / STDERR PDIFF CL ALPHA=0.05;  
  BY byvar; (optional)  
  WHERE condition (optional)  
RUN;  
QUIT;
```

- **The geometric mean is the antilog of the arithmetic mean of the logs:**

```
DATA dset;  
  SET dset old;  
  LOGx = LOG(x);  
RUN;
```

```
PROC UNIVARIATE DATA=dset NOPRINT;  
  VAR LOGx;  
  OUTPUT OUT=outname  
  MEAN=logmean;  
RUN;
```

```
DATA outname;  
  SET outname;  
  geomean = EXP(logmean);  
RUN;
```

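### The primary Cox model is written in conflicting forms: two-level strata as Gaussian random effects in the text, and example code that stratifies on treatment and so yields no hazard ratio

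*SAP*

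**What the plan says.** **Text.** SAP 6.5.1 specifies the primary proportional hazards model "with treatment effect as a fixed effect and stratifying covariates as random effect", and protocol 8.4.2.2.3 (Statistical Methods) has the same: a "proportional hazards regression model with treatment effect as a fixed effect and stratifying covariates as random effect". The random effect is "assumed as a multivariable random gaussian variable with zero mean and diagonal covariance matrix", and "Z is random effect covariate (reflecting randomization strata"). SAP 2.2 identifies those strata: subjects "will be stratified by age and vaccination history and then randomized to one of the two treatment groups".

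**Listed terms.** Later in SAP 6.5.1 the model includes treatment group together with "age strata (2 categories, 6 through 23 months or 24 through 47 months), gender (male or female), vaccination history (yes or no) and country", without saying which are fixed and which random. Further on, the same section says only that country might be added if appropriate. Season is to be adjusted for if the study runs over several seasons.

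**Code.** The Appendix B example for the hazard ratio in all efficacy analyses has `trt agegrp vachis` on the MODEL line, followed by "RANDOM agegrp vachis; STRATA trt". Gender, country and season are absent.

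**Synopsis.** The protocol synopsis writes the hazard ratio in terms of stratum-specific hazards.

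**Fallback.** Penalised likelihood is used if the algorithm does not converge or gives infinite estimates. No rule is given for a variance estimated at zero.

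**The concern.** There are three separate faults.

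1. A normal random effect needs enough levels to learn a variance. With two levels the partial likelihood informs one contrast, so the variance has one degree of freedom. Where the strata enter only as random effects, whether the primary model adjusts for its own randomisation factors then depends on the data.
2. The documents describe at least four models: strata random (SAP 6.5.1, first form), strata as listed terms (SAP 6.5.1, later), strata both fixed and random (Appendix B), and stratum-specific hazards (protocol synopsis). A programmer has to choose.
3. The code that would otherwise settle the choice cannot be run as written to obtain the primary result, because treatment is a stratification variable.

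Primary success is read from the confidence interval of this model, and SAP 6.5.1 also takes the group-sequential information and standard errors from it. That model should be unique and workable before anyone sees unblinded data.

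**Working it through.** **1. The plan's own event counts.** Inputs from SAP 2.3: one-sided alpha 0.0125, power 90%, hazard ratio (HR) 0.6 (1a) and 0.5 (1b), 1:1 allocation. Schoenfeld: D = 4(2.2414 + 1.2816)² / (ln HR)² = 49.65 / (ln HR)².
- 1a: 49.65 / 0.2609 = 190.3, so 191.
- 1b: 49.65 / 0.4805 = 103.3, so 104.

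Both match the plan.

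**2. When a two-level variance is estimated as zero.** Let each level have effect b ~ N(0, σ²). Only the contrast d between levels is identified, and d ~ N(0, 2σ²). Its estimate has standard error s = 1/√(D·p(1−p)), where p is the share in the smaller level. The approximate maximum likelihood (ML) estimate is σ̂² = max{0, (d̂² − s²)/2}, which is zero when |d̂/s| < 1. Hence P(zero) = Φ(1 − d/s) − Φ(−1 − d/s).

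Even split: s = 1/√(191/4) = 0.145 and s = 1/√(104/4) = 0.196.
- No stratum effect: 68% at any D and p.
- Log HR 0.2, 191 events: d/s = 1.38, giving 34%.
- Log HR 0.2, 104 events: d/s = 1.02, giving 47%.

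The documents give neither a stratum HR nor the share previously vaccinated. They require at least 30% of subjects in each age cohort. The range, under assumed values:

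| Events | Smaller level | HR 1.0 | HR 1.25 | HR 1.5 | HR 2 |
|---|---|---|---|---|---|
| 191 | 50% | 68% | 29% | 4% | <1% |
| 191 | 30% | 68% | 33% | 6% | <1% |
| 191 | 10% | 68% | 50% | 24% | 3% |
| 104 | 50% | 68% | 43% | 14% | <1% |
| 104 | 30% | 68% | 46% | 18% | 1% |
| 104 | 10% | 68% | 58% | 39% | 13% |

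If Z were instead one factor with the four stratum cells (3 df), the no-effect figure would be P(χ²₃ < 3) = 61%.

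**3. Precision of the variance.** On 1 df, a chi-square 95% interval runs from 1/5.02 = 0.20 to about 1,018 times the estimate.

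**4. Simulation check.** 600 trials per scenario, Laplace-approximated marginal likelihood, averaging about 181 events (1a) and 98 (1b). Zero-variance rates (age / history) for 1a were 0.69 / 0.70 at HR 1.0, with both zero in 0.49; 0.30 / 0.37 at HR 1.25; and 0.00 / 0.00 at HR 2. These agree with step 2.

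**5. Effect on the treatment estimate.** Same simulations, random versus fixed strata, no stratum effect:
- 1a: mean HR 0.6003 vs 0.6002; mean SE 0.1539 in both.
- 1b: mean HR 0.4961 vs 0.4960; mean SE 0.2160 in both.

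Across all the scenarios run, the largest single-trial difference in log HR was 0.003. In the 600-trial runs rejection rates agreed within 0.2 percentage points. Even omitting the strata altogether at HR 2 moved the mean HR only from 0.5983 to 0.6006.

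**6. Strata both fixed and random, as in Appendix B.** The fixed contrast absorbs the effect. In one simulated data set the marginal log likelihood was −1390.63, −1390.99, −1392.31 and −1394.43 at variances 0.0001, 0.01, 0.1 and 1. The random part is driven to zero and the fixed adjustment stays.

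**7. Treatment in STRATA.** Each event contributes exp(βx + …) divided by the sum of the same expression over its risk set. Stratifying on treatment makes x identical for everyone in that risk set, so exp(βx) cancels. The partial likelihood is flat in β, the information for treatment is zero, and no hazard ratio is produced.

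**The case against.** The best defence is that none of this changes the answer. Randomisation is 1:1 within these strata and attack rates are low, so random, fixed and even unadjusted fits agree closely (step 5). That stands, and it limits the point to specification.

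A reader might infer more than the documents support:

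- *That the variance cannot be estimated at all.* An ML value exists, and is positive whenever the observed contrast exceeds its standard error. It is imprecise.
- *That the strata will usually drop out of the primary analysis.* This holds only for weak stratum effects, where adjustment matters least. Where the factors are also fixed terms, as on the Appendix B MODEL line, they stay adjusted.
- *That a zero variance would trigger penalised likelihood and change the method after the data are seen.* The stated triggers are non-convergence and infinite estimates. A zero variance is neither, and the fallback is itself pre-specified.
- *That treatment standard errors or group-sequential information are compromised by the random effects.* The simulations show no such effect.

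It can also be said that Appendix B is only example code and a programmer would notice the STRATA line. Probably so. But correcting it means choosing a model, and the text does not say which one.

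**Conclusion.** The point holds as a defect of specification. The primary model is stated in forms that conflict. One of them rests each variance on 1 df, and the example code gives no treatment hazard ratio. The zero-variance rates depend on stratum hazard ratios and level shares that are assumed here, and on an ML fit by normal or Laplace approximation. The finding about STRATA on treatment needs none of these assumptions. The efficacy conclusion is not threatened by the random-versus-fixed choice. The gain from repair is a single workable primary model, fixed in advance, that always respects the randomisation factors. It should be repaired, but it is not a reason to doubt the design.

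**What to change.** - Delete the random-effect term from protocol 8.4.2.2.3, SAP 6.5.1 and the Appendix B code.
- Remove `trt` from STRATA and keep it as the fixed effect on the MODEL line.
- Enter age cohort and previous influenza vaccination history as STRATA. This fits the stratum-specific hazards in the protocol synopsis. Fixed covariates are an acceptable alternative, but one form must be named.
- Adjust for season as already planned, and show it in the code.
- State whether gender and country are in the model, and remove the conflict between including country and possibly adding it.
- Make the protocol, SAP 6.5.1 and Appendix B agree before any unblinding, including for an interim analysis.

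The cost is SAP wording and a few lines of code, plus a protocol wording amendment with the approvals set out in protocol 13.4. No data, subjects or events are needed.
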